- ➔ If ANSWER = 4 GO TO WP4C4 (UKB)
- ➔ If ANSWER = 5 GO TO WP4C5 (UKB)
- ➔ IF ANSWER INCLUDES MULTIPLE RESPONSES 1-5 SHOW EACH APPLICABLE WP4C1-5 IN ORDER

Strenuous sports include sports that make you sweat or breathe hard. Heavy DIY includes chopping wood, home or car maintenance, lifting heavy objects or using heavy tools.

[WP4C1 (UKB)]

How many times in the last 4 weeks did you go walking for pleasure?

SELECT one of 8 from 1

- 1 Once in the last 4 weeks
- 2 2-3 times in the last 4 weeks
- 3 Once a week
- 4 2-3 times a week
- 5 4-5 times a week
- 6 Every day
- 1 Do not know
- 3 Prefer not to answer

If the time you spent walking for pleasure varied, please give an average over the past 4 weeks.

[WP4E1 (UKB)]

Each time you went walking for pleasure, about how long did you spend doing it?

SELECT one of 9 from

- 1 Less than 15 minutes
- 2 Between 15 and 30 minutes
- 3 Between 30 minutes and 1 hour
- 4 Between 1 hour and 1½ hours
- 5 Between 1½ hours and 2 hours
- 6 Between 2 and 3 hours
- 7 Over 3 hours
- 1 Do not know
- 3 Prefer not to answer

- ➔ If WP4B1 ANSWER DID NOT INCLUDE 2 OR 3 OR 4 OR 5 GO TO WP11

If the time you spent walking for pleasure varied, please give an average over the past 4 weeks.

[WP4C2 (UKB)]

How many times in the last 4 weeks did you do other exercises such as swimming, cycling, keep fit?

SELECT one of 8 from

- 1 Once in the last 4 weeks
- 2 2-3 times in the last 4 weeks
- 3 Once a week
- 4 2-3 times a week
- 5 4-5 times a week
- 6 Every day
- 1 Do not know
- 3 Prefer not to answer

[WP4E2 (UKB)]

Each time you did other exercises such as swimming, cycling, keep fit, about how long did you spend doing them?

SELECT one of 9 from

- 1 Less than 15 minutes
- 2 Between 15 and 30 minutes
- 3 Between 30 minutes and 1 hour
- 4 Between 1 hour and 1½ hours
- 5 Between 1½ hours and 2 hours
- 6 Between 2 and 3 hours
- 7 Over 3 hours
- 1 Do not know
- 3 Prefer not to answer

➔ **If WP4B1 ANSWER DID NOT INCLUDE 3 OR 4 OR 5 GO TO WP11**

[WP4C3 (UKB)]

How many times in the last 4 weeks did you do strenuous sports?

SELECT one of 8 from

- 1 Once in the last 4 weeks
- 2 2-3 times in the last 4 weeks
- 3 Once a week
- 4 2-3 times a week
- 5 4-5 times a week
- 6 Every day
- 1 Do not know
- 3 Prefer not to answer

[WP4E3 (UKB)]

Each time you did strenuous sports, about how long did you spend doing it?

SELECT one of 9 from

- 1 Less than 15 minutes
- 2 Between 15 and 30 minutes

- 3 Between 30 minutes and 1 hour

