[D2A (UKB)]

What year did you first come to live in the United Kingdom?

Please enter a date in the following format: dd/mm/yyyy

Enter INTEGER

OR

- 1 Do not know

OR

- 3 Prefer not to answer

Please give the year that you FIRST came to live in the United Kingdom. Do not count years if you came to holiday or visit friends or family.

[Y1 (UKB)]

Were you adopted as a child?

SELECT one of 4 from

- | | |
|----|-------------|
| 1 | Yes |
| 0 | No |
| -1 | Do not know |

-3 Prefer not to answer

[Y13 (UKB)]

Is your biological father still alive?

SELECT one of 4 from

1 Yes

0 No

-> GO TO Y13B (UKB)

-1 Do not know

-> GO TO Y13D (UKB)

-3 Prefer not to answer

-> GO TO Y13D (UKB)

[Y13A (UKB)]

What is his age now?

Enter INTEGER

[Require > current age, ≤ 122

Units: years]

OR

-1 Do not know

OR

-3 Prefer not to answer

[Y13B (UKB)]

What was his age when he died?

Enter INTEGER

[Require ≥ 10, ≤ 122

Units: years]

OR

-1 Do not know

OR

-3 Prefer not to answer

[Y13D (UKB)]

Has/did your biological father ever suffer from?

You can select more than one answer

We will ask more details for any type of disorder that you select here

TOGGLE

[Require ≥1 choices]

0 Autoimmune disorder -> GO TO AUTO_A

1 Blood disorders (Anaemia) -> GO TO BLOOD_A

2 Cancer -> GO TO CANC_A

- 4 Digestive system or liver problems -> **GO TO DIG_A**
- 5 Endocrine, nutritional and metabolic disorders (e.g., diabetes, thyroid disorder, vitamin deficiencies) -> **GO TO EN_A**
- 6 Eye or visual problems -> **GO TO EYE_A**
- 7 Fractures, breaks, or joint problems -> **GO TO FRAC_A**
- 8 Heart or circulatory disease (e.g., high blood pressure or stroke) -> **GO TO HEART_A**
- 9 Kidney or urinary system disorders -> **GO TO KIDN_A**
- 10 Lung or respiratory problems -> **GO TO LUNG_A**
- 11 Mental health conditions (e.g. depression, bipolar disorder) -> **GO TO MH_A**
- 12 Neurodevelopmental conditions (e.g., Autism spectrum disorder, ADHD) -> **GO TO ND_A**
- 13 Neurological disorders (things that affect that brain or nervous system) -> **GO TO NEU_A**
- 14 Reproductive system problems -> **GO TO REPRO_A**
- 15 Other not listed -> **GO TO Y16 (UKB)]**
- 16 None of these -> **GO TO Y16 (UKB)]**
- 1 I don't know **[EXCLUSIVE]** -> **GO TO Y16 (UKB)]**
- 3 Prefer not to answer **[EXCLUSIVE]** -> **GO TO Y16 (UKB)]**

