- 13 Neurological disorders (things that affect that brain or nervous system) -> **GO TO NEU_A**
- 14 Reproductive system problems -> **GO TO REPRO_A**
- 15 Other not listed -> **GO TO END SECTION**
- 16 None of these -> **GO TO END SECTION**
- 1 I don't know **[EXCLUSIVE]** -> **GO TO END SECTION**
- 3 Prefer not to answer **[EXCLUSIVE]** -> **GO TO END SECTION**

Answer this question for blood relations only.

Include any sisters or brothers who have died. If you are not sure if your sisters or brothers suffered from any of the listed illnesses, please select 'Do not know'.

If more than one sister or brother has suffered from any of the listed illnesses, you only need to select the illness once.

[AUTO_A_SIB]

Has your brother or sister ever been diagnosed with any of the following autoimmune disorders?

- 0 Rheumatoid arthritis
- 1 Lupus
- 2 Inflammatory Bowel Disease (IBD)
- 3 Multiple Sclerosis (MS)
- 4 Graves' disease
- 5 Guillain-Barre syndrome
- 6 Psoriasis
- 7 Other (not listed)
- 1 I don't know
- 3 Prefer not to answer

[BLOOD_A_SIB]

Has your brother or sister ever been diagnosed with any of the following types of anaemia?

- 0 Iron deficiency anaemia
- 1 Vitamin deficiency anaemia
- 2 Sickle cell anaemia
- 3 Aplastic anaemia
- 4 Thalassemia
- 5 Other (not listed)
- 1 I don't know
- 3 Prefer not to answer

[CANC_A_SIB (CONNECT)]

Which type(s) of cancer specifically were your brother or sister diagnosed with?
Please indicate where the cancer originated, even if it spread to other body areas

- 0 Anal
- 1 Bladder
- 2 Brain
- 3 Breast
- 4 Cervical
- 5 Colon/rectal
- 6 Oesophageal
- 7 Head and neck (Including cancers of the mouth, sinuses, nose, or throat. Not including brain or skin cancers.)
- 8 Gastric

- 9 Kidney
- 10 Leukaemia (blood and bone marrow)
- 11 Liver
- 12 Lung or bronchial
- 14 Lymphoma
- 15 Ovarian
- 16 Pancreatic
- 17 Prostate
- 18 Skin
- 19 Stomach
- 20 Testicular
- 21 Thyroid
- 22 Uterine (endometrial)
- 23 Another type of cancer
- 24 I know they had cancer, but don't know what type
- 1 I don't know
- 3 Prefer not to answer

[CANC_B_SIB (CONNECT)]

What type of skin cancer specifically were your brother or sister diagnosed with?

- 6 Melanoma
- 7 Basal cell
- 8 Squamous cell
- 1 I don't know
- 3 Prefer not to answer

[PREG_A_SIB (CONNECT+ICD)]

What type of complication or difficulties with pregnancy or childbirth has your sister experienced?

- 0 Miscarriage (pregnancy loss before 20 weeks)

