If you are currently taking the pill, select 'Still taking the pill'. If you are unsure, please provide an estimate or select 'Do not know'.

[FH6 (UKB)]

Have you **ever** used hormone replacement therapy (HRT)?

SELECT one of 4 from

1 Yes

0 No -> **GO TO FH9**

-1 Do not know -> **GO TO FH9**

-3 Prefer not to answer -> **GO TO FH9**

[FH6A (UKB)]

How old were you when you first used HRT?

Enter INTEGER

[Require \geq 16, \leq current age]

OR

-1 Do not know

OR

-3 Prefer not to answer

If you are unsure, please provide an estimate or select 'Do not know'.

[FH6B (UKB)]

How old were you when you last used HRT?

Enter INTEGER

[Require \geq FH6A, \leq current age]

OR

-1 Do not know

OR

-11 Still taking HRT

OR

-3 Prefer not to answer

If you are currently using HRT, select 'Still taking HRT'.

If you are unsure, please provide an estimate or select 'Do not know'.

[FH9 (UKB)]

Have you had a hysterectomy (womb removed)?

SELECT one of 4 from

1 Yes

0 No -> GO TO FH10

-5 Not sure -> GO TO FH10

-3 Prefer not to answer -> GO TO FH1

[FH9A (UKB)]

How old were you when you had your hysterectomy?

Enter INTEGER

[Require \geq 0, \leq current age]

OR

-1 Do not know

OR

-3 Prefer not to answer

If you are unsure, please provide an estimate or select 'Do not know'.

[FH10 (UKB)]

Have you had BOTH ovaries removed?

SELECT one of 4 from

1 Yes

0 No -> GO TO L1(UKB)

-5 Not sure -> GO TO L1(UKB)

-3 Prefer not to answer -> GO TO L1(UKB)

Only enter 'Yes' if you have had both ovaries removed

If you are unsure of whether both ovaries have been removed, select 'Do not know'.

[FH10A (UKB)]

How old were you when you had BOTH ovaries removed?

Enter INTEGER

[Require ≥ 0 , \leq current age]

OR

-1 Do not know

OR

-3 Prefer not to answer

[L1 (UKB)]

Have you ever been diagnosed with any of the following by a doctor or other health professional?

Please select all that apply

We will ask more details for any type of disorder that you select here

TOGGLE

[Require ≥ 1 choices]

- 6 Autoimmune disorder -> **GO TO AUTO_A**
- 7 Blood disorders (Anaemia) -> **GO TO BLOOD_A**
- 2 Cancer -> **GO TO CANC_A**
- 3 Complications or difficulties in pregnancy or childbirth -> **SHOW IF FEMALE; GO TO PREG_A**
- 4 Digestive system or liver problems -> **GO TO DIG_A**
- 5 Endocrine, nutritional and metabolic disorders (e.g., diabetes, thyroid disorder, vitamin deficiencies) -> **GO TO EN_A**
- 6 Eye or visual problems -> **GO TO EYE_A**

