- 7 Fractures, breaks, or joint problems -> **GO TO FRAC_A**
- 8 Heart or circulatory disease (e.g. high blood pressure or stroke) -> **GO TO HEART_A**
- 9 Kidney or urinary system disorders -> **GO TO KIDN_A**
- 10 Lung or respiratory problems -> **GO TO LUNG_A**
- 11 Mental health conditions (e.g. depression, bipolar disorder) -> **GO TO MH_A**
- 12 Neurodevelopmental conditions (e.g., Autism spectrum disorder, ADHD) -> **GO TO ND_A**
- 13 Neurological disorders (things that affect that brain or nervous system) -> **GO TO NEU_A**
- 14 Reproductive system problems -> **GO TO REPRO_A**
- 15 Other not listed -> **GO TO L5DF**
- 16 None of these -> **GO TO L5DF**
- 1 I don't know **[EXCLUSIVE]** -> **GO TO L5DF**
- 3 Prefer not to answer **[EXCLUSIVE]** -> **GO TO L5DF**

If the diagnosis was for cancer, please select cancer. We will ask more about the type of cancer in a subsequent question.

[AUTO_A]

Have you ever been diagnosed with any of the following autoimmune disorders by a doctor or other health professional?

- 0 Rheumatoid arthritis
- 1 Lupus
- 2 Inflammatory Bowel Disease (IBD)
- 3 Multiple Sclerosis (MS)
- 4 Graves' disease
- 5 Guillain-Barre syndrome
- 6 Psoriasis
- 7 Other (not listed)
- 1 I don't know
- 3 Prefer not to answer

[BLOOD_A]

Have you ever been diagnosed with any of the following types of anaemia by a doctor or other health professional?

- 0 Iron deficiency anaemia
- 1 Vitamin deficiency anaemia
- 2 Sickle cell anaemia
- 3 Aplastic anaemia
- 4 Thalassemia
- 5 Other (not listed)
- 1 I don't know
- 3 Prefer not to answer

[CANC_A (CONNECT)]

Which type(s) of cancer specifically were you diagnosed with?

Please indicate where the cancer originated, even if it spread to other body areas

- 0 Anal
- 1 Bladder
- 2 Brain
- 3 Breast
- 4 Cervical
- 5 Colon/rectal
- 6 Oesophageal

- 7 Head and neck (Including cancers of the mouth, sinuses, nose, or throat. Not including brain or skin cancers.)
- 8 Gastric
- 9 Kidney
- 10 Leukaemia (blood and bone marrow)
- 11 Liver
- 12 Lung or bronchial
- 14 Lymphoma
- 15 Ovarian
- 16 Pancreatic
- 17 Prostate
- 18 Skin
- 19 Stomach
- 20 Testicular
- 21 Thyroid
- 22 Uterine (endometrial)
- 23 Another type of cancer
- 24 I know I had cancer, but don't know what type
- 1 I don't know
- 3 Prefer not to answer

[CANC_B (CONNECT)]

What type of skin cancer specifically were you diagnosed with?

- 9 Melanoma
- 10 Basal cell
- 11 Squamous cell
- 1 I don't know
- 3 Prefer not to answer

[PREG_A (CONNECT+ICD)]

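### At the four select-all diagnosis gates (L1, Y13D, Y16D, Y19) the skip on 'Other not listed' conflicts with the follow-up of any listed category ticked with it, and 'None of these' is not exclusive

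*Protocol*

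**What the plan says.** L1 (Appendix E, Section 5 of the questionnaire) is a toggle item headed "Please select all that apply", and its stem adds "We will ask more details for any type of disorder that you select here". Each listed category points to its own detail module (AUTO_A, BLOOD_A, CANC_A and so on).

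The last four options all leave the block:
- "15 Other not listed -> GO TO L5DF", with no condition and no exclusive tag;
- "16 None of these -> GO TO L5DF", likewise untagged;
- "I don't know [EXCLUSIVE] -> GO TO L5DF", tagged exclusive;
- the refusal option, also tagged exclusive.

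The family-history gates in Section 4 of the questionnaire repeat the pattern. For the father, Y13D has "15 Other not listed -> GO TO Y16 (UKB"; for the mother, Y16D skips to Y17; for siblings, Y19 has "15 Other not listed -> GO TO END SECTION". Y13D and Y19 carry the same promise of further detail as L1; Y16D does not.

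The physical-activity item WP4B1 (Section 3 of the questionnaire), also select-all, does state what to do with several answers: "IF ANSWER INCLUDES MULTIPLE RESPONSES 1-5 SHOW EACH APPLICABLE WP4C1-5 IN ORDER". Its 'none' option is tagged exclusive, and conditional exits follow each of its follow-up blocks except the last.

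**The concern.** A participant with cancer and, say, eczema has good reason to tick both 'Cancer' and 'Other not listed', because L1 has no skin category. Two instructions then apply at once: show the cancer list, and leave the diagnosis block. The document does not rank them. The second contradicts the stem's promise at L1, Y13D and Y19.

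If it is built so that the skip wins, the missing detail is not missing at random. It falls on people with several conditions, or with relatives who have several, and so would distort self-reported prevalence, comorbidity and family-history variables. Questionnaire completion rates would not show it, because a skipped module looks like a completed questionnaire.

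Separately, because 'None of these' is not exclusive, a record with 'Cancer' and 'None of these' both ticked is accepted. That is a contradictory answer. It does not cause the loss of detail.

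**Working it through.** There is no planned figure to reproduce. The check is a trace of the routing, followed by a look at what Appendix A can say about how often 'Other' might be ticked.

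**Trace at L1: 'Cancer' plus 'Other not listed'.** Cancer points to CANC_A; Other points to L5DF, the medication gate. Neither is conditional.

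- *Reading A: every ticked option's module is shown, then the flow moves on.* CANC_A is asked and nothing is lost. This fits the stem, but the rule is not written.
- *Reading B: the skip prevails.* CANC_A and every other detail module are bypassed. Only the ticks at L1 remain.
- *Reading C: jump to the first module, then run item by item.* The modules have no display conditions and no exits. Someone who ticks only 'Autoimmune' passes through BLOOD_A, CANC_A, DIG_A and all later lists. Most of these (BLOOD_A, CANC_A, DIG_A, EN_A, EYE_A, FRAC_A, HEART_A, KIDN_A, LUNG_A, NEU_A, REPRO_A) offer no 'none' answer. Nothing is skipped, but participants face questions they cannot answer properly.

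Only Reading A delivers what the stem promises, and it is the one not stated. The trace is the same at Y13D, Y16D and Y19, with Y16, Y17 and the end of the section in place of L5DF.

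**Comparison within the questionnaire.** WP4B1 has all three elements that these gates lack: an exclusive 'none', a multi-response rule and conditional exits. At L1 the exclusive tag was applied to two of the four exit options.

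**How plausible is 'Other' as a co-answer?** L1 has no skin, ear or general-infection category. From the 1M column of Appendix A:

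- All conditions: 1,046,245 projected incident diagnoses.
- Skin 52,650, less psoriasis 3,470 (listed under AUTO_A), plus ear 21,670: 52,650 − 3,470 + 21,670 = 70,850; 70,850 / 1,046,245 = 6.8%.
- Infections: 121,435; 121,435 / 1,046,245 = 11.6%.
- Together: (70,850 + 121,435) / 1,046,245 = 192,285 / 1,046,245 = 18.4%.

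Many infections could be ticked under an organ category. Lower respiratory (18,680), urinary (12,360), digestive (8,790) and pelvic inflammatory (3,100) sum to 42,930. The bone, liver, eye, heart, male and other genitourinary, anorectal, other nervous system, chronic hepatitis, tuberculosis and meningitis rows add 4,375, for 47,305 in all (39% of infections). Removing these leaves (192,285 − 47,305) / 1,046,245 = 144,980 / 1,046,245 = 13.9%.

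The range is therefore about 7% (no infections counted as unlisted) to 18% (all counted). These are shares of projected diagnoses over 2.5 years, on Appendix A's assumed uniform ages of 30–79. They are not shares of people ever diagnosed, and not a rate of ticking two options together.

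**The case against.** The best defence is that GO TO is loose shorthand in this appendix, not executable code. Y13D points to AUTO_A, although the father's module is AUTO_A_DAD. MH_A and FH5AA are select-all items whose GO TOs naturally mean 'show this follow-up for this tick'. The option numbering is disordered, perhaps through extraction. A sensible programmer would read the stem and build Reading A. This stands: a reader might infer that people with a listed and an unlisted disease will certainly lose all their disease detail, and the text does not support that. The listed categories carry equally unconditional instructions, no precedence is given, and the category ticks survive even in the worst case.

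It is also fair that own diagnoses have other sources. Linkage is a condition of joining (Section 5) and covers primary care, secondary care, cancer and death data (Section 5.1); L5DF still asks about medication. Prevalent-case exclusion therefore does not rest on these modules alone. No such source is described for relatives.

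A reader might also want a headcount. Assuming that 10% to 30% of 5 million tick both would give 0.5 to 1.5 million. Nothing in the documents supports that rate, and the product also presumes that the skip prevails.

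The shorthand defence does not remove the conflict. The authors wrote the rule out at WP4B1, so its absence here cannot be read as a settled convention. Nor can the pilots be taken as having tested this routing: Section 3.6 says they used the initial version, and that the later changes, which touch the health and family history sections, are those in Appendix E.

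**Conclusion.** The point holds as a routing conflict: wrong as written at L1, Y13D, Y16D and Y19, below must-fix in severity. The skip on 'Other not listed' contradicts the follow-up instructions of any listed category ticked with it and, at L1, Y13D and Y19, the stem's own promise. No precedence or multi-response rule resolves this. 'None of these' accepts contradictory answers.

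The consequence is conditional. Only if the skip is programmed to prevail is named-disease detail lost, and then for participants who report a listed plus an unlisted condition. For own diagnoses, linkage would recover part of it; for relatives' diagnoses the protocol describes no other source. The size of the affected group cannot be derived from the documents. The 7% to 18% from Appendix A supports nothing beyond 'Other' being a plausible co-answer.

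**What to change.** At all four gates:

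1. Tag 'None of these' as exclusive.
2. Let 'Other not listed' exit the block only when no listed category is ticked.
3. Add a rule of the WP4B1 kind: show each applicable module in order, then go to L5DF (L1), Y16 (Y13D), Y17 (Y16D) or the end of the section (Y19).

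The cost is a routing edit and a re-test of four items, with no new question. The test script should include a listed category plus 'Other', two listed categories, and one category alone. L5DF also has an untagged 'None of these' and no multi-response rule, and could be checked at the same time. If the short questionnaire (Section 3.7) reuses these items, it should take the corrected routing. The edit is best made before fielding, since detail not asked at baseline could be recovered only by re-contact or, for own diagnoses, in part by linkage.

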What type of complication or difficulties with pregnancy or childbirth have you experienced?

- 0 Miscarriage (pregnancy loss before 20 weeks)
- 1 Stillbirth (pregnancy loss after 20 weeks)
- 2 Live birth and still birth (loss of one or more multiples)
- 3 Ectopic or tubal pregnancy
- 4 Trying to get pregnant for more than a year but not getting pregnant during that time
- 5 hyperemesis gravidarum
- 6 Gestational diabetes
- 7 Preterm labour and delivery
- 8 Complicated labour and delivery
- 9 Traumatic labour or delivery
- 10 Pre-eclampsia

- 11 Eclampsia
- 12 Gestational hypertension
- 13 Other (not listed)
- 1 I don't know
- 3 Prefer not to answer

[DIG_A (CONNECT)]

Have you ever been diagnosed with any of the following digestive system problems by a doctor or other health professional?

- 0 Gastro-oesophageal Acid Reflux (GORD)
- 1 Barrett's Oesophagus
- 2 Irritable bowel syndrome
- 3 Inflammatory Bowel Disease
- 4 Diverticulitis or Diverticulosis
- 5 Ulcerative Colitis
- 6 Crohn's Disease
- 7 Coeliac Disease (also known as Gluten-Sensitive Enteropathy)
- 8 Gallstones (Biliary Stones)
- 9 Fatty liver disease
- 10 Liver Cirrhosis
- 11 Hepatitis
- 12 Pancreatitis
- 5 Other (not listed)
- 1 I don't know
- 3 Prefer not to answer

[EN_A]

Have you ever been diagnosed with the following conditions by a doctor or health professional?

- 0 Type 1 diabetes
- 1 Type 2 diabetes
- 2 overactive thyroid
- 3 underactive thyroid
- 4 Cushing syndrome
- 5 Lactose intolerance
- 6 Vitamin A deficiency
- 7 Thiamine deficiency
- 8 Vitamin D deficiency
- 3 Other (not listed)
- 1 I don't know
- 3 Prefer not to answer

[EYE_A]

Have you ever been diagnosed with any of the following eye or visual problems by a doctor or other health professional?

- 3 Glaucoma
- 1 Visual impairment including blindness
- 2 Double vision
- 3 Night blindness
- 4 Colour blindness
- 5 Macular degeneration
- 6 Cataracts
- 7 Retinal detachment
- 8 Diabetic retinopathy
- 9 Other (not listed)
- 1 I don't know
- 3 Prefer not to answer

[FRAC_A]

What type of fractures, breaks, joint or bone problems have you experienced?

- 45 Hip fracture
- 1 Osteoporosis
- 2 Osteoarthritis (arthritis)
- 3 Gout
- 4 Other (not listed)
- 1 I don't know
- 3 Prefer not to answer

[HEART_A (CONNECT)]

Have you ever been diagnosed with any of the following heart or circulatory diseases by a doctor or other health professional?

- 0 B-12 Deficiency (Pernicious Anaemia)
- 1 Coronary Artery/Coronary Heart Disease

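### Rheumatoid arthritis, MS and psoriasis can be recorded by name only through an unexplained autoimmune heading, so respondents who do not see them as autoimmune can misfile them, and for relatives no linkage repairs this

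*Protocol*

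**What the plan says.** Section 5 of the baseline questionnaire (Appendix E) asks at item L1 for broad disease headings and then opens a detailed list for each heading ticked. One heading is "Autoimmune disorder". It opens AUTO_A, which asks "Have you ever been diagnosed with any of the following autoimmune disorders by a doctor or other health professional" and names, among others, "Rheumatoid arthritis", multiple sclerosis and psoriasis. None of the three is named in any other diagnosis list.

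Two other headings plausibly attract the same people:

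- "Fractures, breaks, or joint problems" opens FRAC_A, which offers hip fracture, osteoporosis, "Osteoarthritis (arthritis", gout and an other option.
- "Neurological disorders (things that affect that brain or nervous system" opens NEU_A, which offers epilepsy, Parkinson's disease, three dementia options, two migraine options and an other option.

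There is no skin heading. The other-not-listed choice at L1 moves on to medications and asks nothing further.

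Section 4 (family history) repeats this structure for the father (Y13D), mother (Y16D) and siblings (Y19), each with its own AUTO_A, FRAC_A and NEU_A list.

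The introduction to Section 1 of the questionnaire tells respondents to pick the nearest option when no exact one exists. It also offers a button to go back and change answers.

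**The concern.** A two-step question records a disease correctly only if the respondent picks the heading under which it has been filed. For these three diseases that heading is a mechanism (autoimmunity), while most other headings are organ systems that people associate with their symptoms. A respondent who thinks of rheumatoid arthritis as a joint disease, MS as a disease of the nervous system or psoriasis as a skin disease is thinking along the lines of the protocol's own Appendix A, yet does not reach the list that names it.

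What is at stake is the sensitivity of the self-reported item. It matters most for family history. Protocol section 3.6 says the questionnaire is meant to capture what linkage cannot easily supply, and the linkages in sections 2.6 and 5.1 concern participants. No linked source is described for parents or siblings, so a relative's disease filed wrongly here stays wrong.

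**Working it through.** **Where each disease is filed, and where it goes otherwise.** The same pattern holds for self, father, mother and siblings.

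| Disease | Class in Appendix A | Named in | If only the organ route is taken |
|---|---|---|---|
| Rheumatoid arthritis | Musculoskeletal | AUTO_A only | FRAC_A: osteoarthritis glossed as arthritis, or other |
| Multiple sclerosis | Neurological | AUTO_A only | NEU_A: other |
| Psoriasis | Skin | AUTO_A only | No skin heading: other not listed, no follow-up |
| Inflammatory bowel disease (comparison) | – | AUTO_A and DIG_A | DIG_A: named correctly |

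The last row shows that the instrument already has the remedy. "Inflammatory Bowel Disease" is offered under both the autoimmune and the digestive heading.

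**Which errors are possible.**

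1. Rheumatoid arthritis is the one case where a wrong named answer is on offer. The gloss on osteoarthritis equates it with arthritis in general, and the instruction to take the nearest answer points the same way.
2. For MS and psoriasis the result is an unnamed other entry, so the diagnosis is lost but no other disease gains it.
3. The autoimmune heading has no examples. The endocrine, heart, mental health and neurodevelopmental headings do have them.
4. For the participant, the medication section offers a partial second route, but its list of anti-rheumatic drugs is also reached through an autoimmune heading. There is no medication section for relatives.

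**Scale, as an illustration only.** The document gives neither a sensitivity for these items nor a prevalence of family history, so both are assumed here. Let the exposure be a family history with true control prevalence p0. Then p1 = OR·p0/(1 − p0 + OR·p0) among cases. With sensitivity s and specificity 1, the recorded proportions are s·p1 and s·p0. With 5,000 cases and 4 controls per case (the Table 2 layout), solve

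s·p1 − s·p0 = z(α)·SE0 + z(0.80)·SE1,

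where SE0 is the pooled and SE1 the unpooled standard error of the difference.

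Baseline check at s = 1 and critical p-value 0.05: Table 2 gives 1.41 at 1% prevalence and 1.26 at 2.5%. This formula gives 1.49 and 1.30 two-sided, and 1.43 and 1.27 one-sided. The one-sided form is closer to the table, so only the change down each column should be read.

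| Assumed s | 1%, two-sided | 1%, one-sided | 2.5%, two-sided | 2.5%, one-sided |
|---|---|---|---|---|
| 1.0 | 1.49 | 1.43 | 1.30 | 1.27 |
| 0.9 | 1.51 | 1.45 | 1.32 | 1.28 |
| 0.7 | 1.59 | 1.52 | 1.37 | 1.32 |
| 0.5 | 1.71 | 1.63 | 1.44 | 1.39 |

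The minimum detectable odds ratio hardly moves if few respondents go astray, and moves noticeably only if sensitivity falls a long way.

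**The case against.** The best defence is that the instrument lets an informed respondent answer correctly. L1 is select-all, the autoimmune heading comes first, and anyone who ticks it sees all three diseases by name. A respondent who meets a list without their disease can go back and add the heading. FRAC_A and NEU_A both have an other option, so nobody is forced into osteoarthritis, and the help text for parents says to mark only illnesses one is sure of. For participants themselves, linked primary and secondary care records give a separate source of diagnoses. Section 3.6 also reports cognitive testing, pilots with over 1,500 completed questionnaires and review by the Scientific Advisory Board.

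Most of this stands, and it limits the point. A reader might infer that these diseases are in fact being misreported or lost on a known scale. The document does not support that: it shows a route by which it can happen and no rate. Nor can Appendix A supply one, because its counts are 2.5-year incident diagnoses from coded records, while the item asks about diagnoses ever made. A reader might also infer that the loss follows education; nothing in the document speaks to that.

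The defence does not remove the mechanism. Going back helps only someone who realises that the disease sits under another heading. The testing is reported without any result on these lists. Linkage does not reach relatives.

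**Conclusion.** The point holds in conditional form. Respondents who do not recognise rheumatoid arthritis, MS or psoriasis as autoimmune, and so tick only an organ heading or the other option, can record the first as osteoarthritis, the second as an unspecified neurological disorder and the third as an unspecified condition. The effect is lost sensitivity for the three named diseases, chiefly in family history. The document gives no basis for putting a percentage on it.

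The stronger reading, that osteoarthritis data are seriously contaminated, is not supported either. Appendix A lists far more osteoarthritis (31,380 incident diagnoses per million) than rheumatoid arthritis (2,650). Those counts are only a rough guide to lifetime diagnoses, but they suggest that the smaller category has more to lose.

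The conclusion rests on two things: the routing as printed in Appendix E, and the assumption that some respondents think of these diseases by organ. This is an improvement worth making, not a threat to the cohort.

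**What to change.** In the self, father, mother and sibling versions:

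1. Add examples to the heading: *Autoimmune disorder (e.g., rheumatoid arthritis, multiple sclerosis, psoriasis)*. This also covers psoriasis, so no new skin heading is needed.
2. Add rheumatoid arthritis to FRAC_A and multiple sclerosis to NEU_A, as is already done for inflammatory bowel disease.
3. Remove the bracketed gloss from the osteoarthritis option.
4. State in the data dictionary that a tick in either list counts as the same diagnosis.

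The cost is slightly longer lists in a questionnaire that averages 35 minutes, plus one de-duplication rule. The change is best made early: answers on relatives already collected cannot be corrected without going back to the participant, and the short questionnaire in section 3.7 will draw its items from this one.
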